**b) Describe any animal experimentation and findings leading to the formulation of the study.**

Animal analogues, primarily rats, have been used in the testing of rTMS. Results from these studies have been crucial in establishing the safety parameters for use with humans.

**4. Radioisotopes or Radiation Machines**

**a) List all standard of care procedures using ionizing radiation (radiation dose received by a subject that is considered part of their normal medical care). List all research procedures using ionizing radiation (procedures performed due to participation in this study that is not considered part of their normal medical care). List each potential procedure in the sequence that it would normally occur during the entire study. More Info**

Identify Week/Month of study	Name of Exam	Identify if SOC or Research
	X-ray (for MRI)	Research

**b) For research radioisotope projects, provide the following radiation-related information:**

**Identify the radionuclide(s) and chemical form(s).**

**Title :** Repetitive Transcranial Magnetic Stimulation to Improve Cognitive Function in TBI  
**Approval Period:** 12/11/2018 - 02/13/2019

N/A

**For the typical subject, provide the total number of times the radioisotope and activity will be administered (mCi) and the route of administration.**

N/A

**If not FDA approved provide dosimetry information and reference the source documents (package insert, MIRD calculation, peer reviewed literature).**

N/A

**c) For research radiation machine projects, provide the following diagnostic procedures:**

**For well-established radiographic procedures describe the exam.**

For MRI screening, a skull x-ray or other radiologic procedure might be obtained if the subject reports the possibility that there is metal in the body. This will be done at the radiologist's discretion, and is likely to be infrequent.

**For the typical subject, identify the total number of times each will be performed on a single research subject.**

If an MRI X-ray screen is indicated, for a typical subject only one X-ray would be performed.

**For each radiographic procedure, provide the setup and technique sufficient to permit research subject dose modeling. The chief technologist can usually provide this information.**

These infrequent procedures will be at the radiologist's discretion. The radiation exposure from such x-rays is equivalent to that occurring from natural sources over two months, and increases the risk of cancer by 1/250,000.

**For radiographic procedures not well-established, provide FDA status of the machine, and information sufficient to permit research subject dose modeling.**

N/A

**d) For research radiation machine projects, provide the following therapeutic procedures:**

**For a well-established therapeutic procedure, identify the area treated, dose per fraction and number of fractions. State whether the therapeutic procedure is being performed as a normal part of clinical management for the research participants' medical condition or whether it is being performed because the research participant is participating in this project.**

N/A

**For a therapeutic procedure that is not well-established, provide FDA status of the machine, basis for dosimetry, area treated, dose per fraction and number of fractions.**

N/A

**5. Devices**

**a) Please list in the table below all Investigational Devices (including Commercial Devices used off-label) to be used on participants.**

**5.1 Device Name : rTMS Device**

**Describe the device to be used.**

The MagPro X100 is an advanced, high performance magnetic stimulator.  
**Applications:**  
--Is often used within Transcranial Magnetic Stimulation (TMS) and

**Title :** Repetitive Transcranial Magnetic Stimulation to Improve Cognitive Function in TBI  
**Approval Period:** 12/11/2018 - 02/13/2019

**repetitive Transcranial Magnetic Stimulation (rTMS) research**  
**--Examination of human cortical physiology**  
**--Examination of the physiology of the motor pathways in the central and peripheral nervous system**  
**--Examination of functional aspects of motor nerve stimulation**  
**Features:**  
**--3 waveforms: Biphasic, Biphasic Burst and Monophasic**  
**--Selectable current direction**  
**--Stimulation rates up to 100 pulses per second**  
**--Programmable input/output triggers**  
**--System operation control via a built-in computer, eliminating the need for an external computer to set up and control the timing of stimulus sequences**  
**--Flexible protocol storage in built-in computer**

**Manufacturer :** Magventure

**Risk :** Non-significant

Y I confirm the above are true.

**Rationale for the device being non-significant risk:**

After a decade of research, rTMS is generally regarded as safe and without lasting side effects if established guidelines are followed (Janicak et al., 2008; Machii et al., 2006). There have been no significant cognitive (Triggs et al., 1999; Little et al., 2000), neurological (Nahas et al., 2000) or cardiovascular sequelae reported as a result of rTMS. See answer to 9 A.

**Sponsor of Project**

**Indicate who is responsible for submitting safety reports to the FDA:**

Y The sponsor is a non-STANFORD investigator or group.

**Ordering, Storage and Control**

**To prevent the device being used by a person other than the investigator, and in someone other than a research participant: Confirm that the device will be handled according to the SHC/LPCH policy for Investigational New Devices or as appropriate. If no, please provide an explanation. :**

Y Confirm?  
\_\_\_\_\_

b) Please list in the table below all IDE Exempt Devices (Commercial Device used according to label, Investigational In Vitro Device or Assay, or Consumer Preference/Modifications/Combinations of Approved Devices) to be used on participants.

**Title :** Repetitive Transcranial Magnetic Stimulation to Improve Cognitive Function in TBI  
**Approval Period:** 12/11/2018 - 02/13/2019

## 6. Drugs, Reagents, or Chemicals

- a) Please list in the table below all investigational drugs, reagents or chemicals to be administered to participants.
- b) Please list in the table below all commercial drugs, reagents or chemicals to be administered to participants.

## 7. Medical Equipment for Human Subjects and Laboratory Animals

**If medical equipment used for human patients/participants is also used on animals, describe such equipment and disinfection procedures.**

No equipment that is used on humans is also used on animals.

## 8. Participant Population

- a) **State the following: (i) the number of participants expected to be enrolled at Stanford-affiliated site(s); (ii) the total number of participants expected to enroll at all sites; (iii) the type of participants (i.e. students, patients with certain cancer, patients with certain cardiac condition) and the reasons for using such participants.**

(i) 100 participants are expected to be enrolled  
(ii) 100 participants at VAPAHCS  
(iii) all participants will be Veterans, Military personnel and Civilians.

- b) **State the age range, gender, and ethnic background of the participant population being recruited.**

Age range: 20-65 years  
Note: We may include participants between 65-70 if they contact us and pass the screening (and are not showing cognitive decline related to dementia)  
Gender: Males and Females  
Ethnic Background: Any race or ethnic origin

- c) **State the number and rationale for involvement of potentially vulnerable subjects in the study (including children, pregnant women, economically and educationally disadvantaged, decisionally impaired, homeless people, employees and students). Specify the measures being taken to minimize the risks and the chance of harm to the potentially vulnerable subjects and the additional safeguards that have been included in the protocol to protect their rights and welfare.**

Children, pregnant women, economically and educationally disadvantaged, decisionally impaired, and homeless people will not be recruited for this protocol.

- d) **If women, minorities, or children are not included, a clear compelling rationale must be provided (e.g., disease does not occur in children, drug or device would interfere with normal growth and development, etc.).**

There will be no participation of children in this study.

- e) **State the number, if any, of participants who are laboratory personnel, employees, and/or students. They should render the same written informed consent. If payment is allowed, they should also receive it. Please see Stanford University policy.**

It is unlikely that any laboratory personnel, employees, or students will qualify for participation in this study. If any do qualify and wish to participate, they will be treated the same as any other participant.

**Title :** Repetitive Transcranial Magnetic Stimulation to Improve Cognitive Function in TBI  
**Approval Period:** 12/11/2018 - 02/13/2019

- f) **State the number, if any, of participants who are healthy volunteers. Provide rationale for the inclusion of healthy volunteers in this study. Specify any risks to which participants may possibly be exposed. Specify the measures being taken to minimize the risks and the chance of harm to the volunteers and the additional safeguards that have been included in the protocol to protect their rights and welfare.**

Participants should all be in fair physical health though may be cognitively impaired as seen in the chronic symptoms of mild/moderate TBI (note we have removed the 1 SD or more below the mean score on Trail Making Test B (TMT B) criteria from our inclusion criteria). All procedures are considered low risk or standard of care.

- g) **How will you identify participants for recruitment? (E.g., by: chart review; referral from treating physician; response to ad). Attach recruitment materials in Section #16 (Attachments). All Final or revised recruitment materials, flyers, etc. must be submitted to the IRB for review and approval before use. You may not contact potential participants prior to IRB approval. See Advertisements: Appropriate Language for Recruitment Material.**

Based on the team established, we will recruit from: War Related Illness and Injury study Center (WRIISC) at VAPA (one of the three in the nation tasked to address complex problems faced by Veterans of the recent wars; PI: [name], PhD, Deputy Director Research), Polytrauma VAPA (Co-I: [name]; one of the 5 polytrauma network sites the country and a participating DVBIC site), Memory clinics at VAPA as well as from the surrounding VA clinics. Letters will be sent to patients and providers with information about the study, and a pre-paid response postcard. Phone calls will be made to these Veterans as followup within two weeks. Flyers will be posted in relevant clinic settings and on the Stanford University Marguerite Shuttle, and study information will be advertised on social media, including facebook. (We plan to recruit an average of 2.2 patients/month to meet our target enrollment of 40 participants in 18 months).

- h) **Inclusion and Exclusion Criteria.**

**Identify inclusion criteria.**

**Inclusion Criteria**

- Age 20-65 years (we may accept participants who pass the screening between 65-70)
- History of (Post Traumatic Amnesia < 1 day for mild TBI; 1 day > x < 7days for moderate TBI)
- Ability to obtain a Motor Threshold (MT) will be determined during the screening process.
- If on a psychotropic medication regimen, that regimen will be stable for at least 4 weeks prior to entry to the study and patient will be willing to remain on a stable regimen during the acute treatment phase.
- Has an adequately stable condition and environment to enable attendance at scheduled clinic visits.
- For female participants, agrees to use one of the following acceptable methods of birth control: abstinence, oral contraceptive; Norplant etc.
- Able to read, verbalize understanding, and voluntarily sign the Informed Consent Form prior to participating in any study-specific procedures or assessments.

**Identify exclusion criteria.**

**Exclusion Criteria**

- Pregnant or lactating female.
- Unable to be safely withdrawn, at least two-weeks prior to treatment commencement, from medications that substantially increase the risk of having seizures
- Have a cardiac pacemaker or a cochlear implant
- Have an implanted device (deep brain stimulation) or metal in the brain (see standard MRI exclusion criteria including metal screening section in telephone screen, Appendix A).
- Have a mass lesion, cerebral infarct or other active CNS disease, including a seizure disorder.
- Known current psychosis as determined by DSM-IV coding in chart (Axis I, psychotic disorder, schizophrenia) or a history of a non-mood psychotic disorder.
- Diagnosis of Bipolar Affective Disorder I (as determined by chart review and intake interview)
- Current amnesic disorders, dementia, MOCA ≤ 16, or delirium.
- Current substance abuse (not including caffeine or nicotine) as determined by positive toxicology screen, or by history via AUDIT, within 3 months prior to screening
- Prior history of seizures

**Title :** Repetitive Transcranial Magnetic Stimulation to Improve Cognitive Function in TBI  
**Approval Period:** 12/11/2018 - 02/13/2019

- Severe TBI or open head injury
- TBI within last two months or in acute stage
- Participation in another concurrent clinical trial
- Patients with prior exposure to rTMS (NOTE: TMS is allowed)
- Active current suicidal intent or plan. Patient at risk for suicide will be required to establish a written safety plan involving their primary psychiatrist and the treatment team before entering the clinical trial

**i) Describe your screening procedures, including how qualifying laboratory values will be obtained. If you are collecting personal health information prior to enrollment (e.g., telephone screening), please request a waiver of authorization for recruitment (in section 15).**

Research Assistants will assess for participant eligibility in a telephone screen. Telephone screening will assess a potential participant's background, demographics, health questions, and psychiatric stability. Study Personnel will meet once per week to review, discuss, and make determinations about the appropriateness of potential participants for the study.

If by study midpoint (approximately end of year one) we are unable to get 20 participants per year, we will reconsider inclusion/exclusion criteria.

Patients who are screened over the telephone for possible eligibility for the study will be listed on the Patient Screening Log. Note: we will make all our efforts to screen patients for both rTMS and MRI exclusions but as our primary aim is to test rTMS for use in TBI population, we will enroll participants in the study who are ineligible to be in the MRI scanner but eligible for rTMS treatment. After the patient signs the Informed Consent Form, the on-site screening procedures and assessments can be initiated.

Data will be collected on paper forms and questionnaires, and entered into encrypted, password-protected databases located on physically secure VA servers behind a firewall. All types of data collected will be de-identified according to the VHA Privacy Handbook 1200.12. Each subject will be assigned a subject ID (SUBID). The SUBID codebook will be maintained by the PI, and will be available to appropriate members of the research team but kept in a locked file cabinet or in an encrypted, password-protected file on a physically secure, password protected computer at VAPA.

All research personnel involved in this study will have successfully completed all applicable VA, and Stanford training. All subject-level identifiable data will be treated as Protected Health Information (PHI) unless that data does NOT contain any of the data elements that HIPAA considers protected. No sensitive data or PHI will be stored on any device other than the secure server. Paper forms will be stored in locked file cabinets in locked offices.

Data from the rTMS study will be entered into a designed ACCESS database and maintained on a VA server located at VAPA, password protected, encrypted and no PHI will be present.

**j) Describe how you will be cognizant of other protocols in which participants might be enrolled. Please explain if participants will be enrolled in more than one study.**

We will ask the potential subject if they are participating in any other protocols. They will be instructed not to participate in any other protocols during their involvement with our study without first getting prior authorization from both our research team and that of the other study. Overlapping participation will be handled on a case-by-case basis.

**k) Payment/reimbursement. Explain the amount and schedule of payment or reimbursement, if any, that will be paid for participation in the study. Substantiate that proposed payments are reasonable and commensurate with the expected contributions of participants and that they do not constitute undue pressure on participants to volunteer for the research study. Include provisions for prorating payment. See payment considerations**

There will no longer be payment for participation in this study.

**l) Costs. Please explain any costs that will be charged to the participant.**

**Title :** Repetitive Transcranial Magnetic Stimulation to Improve Cognitive Function in TBI  
**Approval Period:** 12/11/2018 - 02/13/2019

There are no costs to participants other than time and inconvenience.

**m) Estimate the probable duration of the entire study. Also estimate the total time per participant for: (i) screening of participant; (ii) active participation in study; (iii) analysis of participant data.**

Duration of the study: 2 years

Total time per participant for all screening: 7-8 hours.

For active participation in the study -

- Baseline: approximately 8 hours on-site with MRI, labs, clinical exams
- Intervention: approx. 30-60 minutes/session, 20 sessions over 2 -6 weeks, depending on scheduling
- Follow-up: one follow-up visits over 6 months, each visit lasting approx. 8.5 hrs

Analysis of participant data immediately post treatment and at 6 month follow-up

**9. Risks**

- a) For the following categories include a scientific estimate of the frequency, severity, and reversibility of potential risks. Wherever possible, include statistical incidence of complications and the mortality rate of proposed procedures. Where there has been insufficient time to accumulate significant data on risk, a statement to this effect should be included. (In describing these risks in the consent form to the participant it is helpful to use comparisons which are meaningful to persons unfamiliar with medical terminology.)

**The risks of the Investigational devices.**

MagVenture MagPro X100 - see rTMS risks under "procedures" below.

**The risks of the Investigational drugs. Information about risks can often be found in the Investigator's brochure.**

n/a

**The risks of the Commercially available drugs, reagents or chemicals. Information about risks can often be found in the package insert.**

n/a

**The risks of the Procedures to be performed. Include all investigational, non-investigational and non-invasive procedures (e.g., surgery, blood draws, treadmill tests).**

rTMS - rTMS Safety especially for Mild and Moderate TBI Veterans

After a decade of research, rTMS is generally regarded as safe and without lasting side effects if established guidelines are followed (Janicak et al., 2008; Machii et al., 2006). There have been no significant cognitive (Triggs et al., 1999; Little et al., 2000), neurological (Nahas et al., 2000) or cardiovascular sequelae reported as a result of rTMS.

The primary safety concern with rTMS, in any population, has been the risk of seizure induction. Eight seizures have been reported secondary to rTMS (Wassermann, 1998). These have occurred in a sample size estimated to be over several thousand rTMS treatment sessions. The rTMS community has adopted and widely used the guidelines prescribing a safe interval between pulse trains (Gerloff et al., 1997) and the safety guidelines from a National Institute of Neurological Disorders and Stroke (NINDS) workshop on rTMS. To our knowledge there have been two publications since 1997 describing events during rTMS that might be considered seizures. Conca and colleagues reported a patient who experienced a 'pseudoabsence seizure'. It is unclear if this was a true seizure (Conca et al., 2000). Bernabeu and colleagues reported on a patient who had a seizure during rTMS. In this case, there was a brief interstimulus interval (Bernabeu et al., 2004). The risk of seizures for rTMS treatment is less than 1%.

How does this impact our study: The current safety guidelines have not been tested for mild and moderate TBI population which is precisely the purpose of this pilot grant. In TBI population, posttraumatic epilepsy

**Title :** Repetitive Transcranial Magnetic Stimulation to Improve Cognitive Function in TBI  
**Approval Period:** 12/11/2018 - 02/13/2019

is the most common delayed sequelae of TBI. But this incidence is very low (about 5%) in TBI patients with closed head injury (Ropper et al., 2005) who are most likely our mild and moderate TBI patients. In a clinical setting, for example in Polytrauma Transitional Rehabilitation Program (PTRP – VAPA) the expected recovery trajectory for persons with mTBI is full cognitive recovery in 3-6 months following injury. Persisting or worsening cognitive status is often related to other co-morbid psychiatric issues, such as depression and PTSD, chronic pain, sleep apnea (all will be) used as covariates in our analysis). Including persons with moderate TBI in our study would likely allow for examination of rehabilitation treatment effects on cognitive functioning for those who tend to have persisting cognitive difficulties following injury. On PTRP, patients are often admitted from the acute inpatient rehab unit on anticonvulsant medications if they had a seizure 1 day or more following the injury. Typically, if the patient experienced a seizure immediately at the scene of the incident, they are not considered at a greater risk for subsequent seizures. For those who do not have a history of seizures following injury, they are not considered at a greater risk of subsequent seizures and are not placed on anticonvulsant medications. Importantly, the interval between the head injury and the first seizure varies greatly (Demirtas-Tatlidede et al., 2012) and must be considered as a variable for recruitment in this study. Currently PTRP houses patients 2 months to 2 years post TBI. Note, that there is only one case study which performed detailed safety assessments and reported a lack of adverse events in a patient with severe TBI following application of a specific rTMS protocol over 5 consecutive days through 6 weeks (Pape et al., 2009). Our protocol will be highly stringent and will exclude any severe TBI patients (including those with any fractures, metal plates or open head injuries), acute patients or those who have had a concussion within the last 2 months, and those who have a history of seizures of any type.

Neuropsychology testing - The risks posed by neuropsychological testing are mild frustration and mild fatigue that will not persist.

MRI - The study participant may get a metal taste in their mouth or some tingling in their hands or feet during the MRI scan. Occasionally, individuals experience claustrophobia (fear of confinement in a small space) during the MRI scan.

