**Secondary Hypotheses:**

1. Sustained Improvement. At the end of the 6-month post treatment follow-up, TBI patients who received rTMS would be more likely to continue to have reduced symptoms, i.e. greater "executive function improvement" than patients who received sham rTMS.
2. Secondary consequences of TBI will improve with rTMS treatment, i.e. scores on Quality of Life (QOL) scale will show significantly greater improvement in patients with mild to moderate TBI who received rTMS treatment.
3. Moderators of Response. Age, severity of symptoms at baseline, type of comorbidity (PTSD, time since injury, sleep, depression substance abuse, medication use, cognitive exercises, fatigue or any combinations of these), TBI type, duration of

**Title :** Repetitive Transcranial Magnetic Stimulation to Improve Cognitive Function in TBI  
**Approval Period:** 12/11/2018 - 02/13/2019

illness and prior treatment resistance (rTMS/ECT): may affect or "moderate" treatment response.

4. Greater functional connectivity will be observed in hub centers of the Default Mode Network (DMN), particularly the precuneus/posterior cingulate area as measured by resting state fMRI at follow-up compared to baseline in those TBI patients treated with rTMS compared to those treated with sham.

5. Mediators of Response to Treatment: to establish a preliminary understanding of the underlying mechanisms related to rTMS modulation of synaptic repair in TBI we will also look at Brain Derived Neurotrophic Factor (BDNF) plasma samples in our population.

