#### B. Secondary Objectives

1. To evaluate the durability of benefit of rTMS in treatment of executive function deficits (patients receiving rTMS are more likely to show significant improvement at 6 months post treatment than those receiving sham).

2. To evaluate post treatment the impact of rTMS treatment on everyday functioning as defined by the Quality of Life (QOL) scale, a frequently used clinical measure.

3. To evaluate other moderators of response to rTMS treatment such as age, time since injury and severity of PTSD (assessed by PCL-checklist score) as well as depression, sleep substance abuse, fatigue or any combinations of these factors.

4. To evaluate resting state functional MRI (fMRI) as a biological marker of response to rTMS treatment.

5. To evaluate underlying biological mechanisms involving BDNF in synaptic repair and/or change in network connectivity resulting from rTMS treatment.

6. To evaluate improvement in headaches and pain reporting following rTMS treatment using responses on the assessment HIT-6 (HIT-6 has been included with the original protocol on Section 16)

- c) **Explain why human subjects must be used for this project. (i.e. purpose of study is to test efficacy of investigational device in individuals with specific condition; purpose of study is to examine specific**

**Title :** Repetitive Transcranial Magnetic Stimulation to Improve Cognitive Function in TBI  
**Approval Period:** 12/11/2018 - 02/13/2019

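### Mild TBI participants can enter before the protocol expects natural recovery to be complete, yet time since injury is not among the covariates the protocol names

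*Protocol*

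**What the plan says.** **Entry.** The exclusion criteria (section 8h) rule out "TBI within last two months or in acute stage". Section 9a repeats the limit by excluding "acute patients or those who have had a concussion within the last 2 months". No later minimum is set for mild TBI.

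**Natural recovery.** Section 9a says that in a clinical setting "the expected recovery trajectory for persons with mTBI is full cognitive recovery in 3-6 months following injury". It contrasts this with moderate TBI, where difficulties tend to persist. It also describes the transitional rehabilitation programme of the polytrauma service: "Currently PTRP houses patients 2 months to 2 years post TBI". Polytrauma is one of the recruitment sources in section 8g.

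**Population.** Section 8f expects that participants may be "cognitively impaired as seen in the chronic symptoms of mild/moderate TBI". It also records that the requirement for a low baseline Trail Making B score was dropped.

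**Analysis.** In the same paragraph as the recovery statement, section 9a says: "depression and PTSD, chronic pain, sleep apnea (all will be) used as covariates in our analysis". Time since injury is not in that list. It appears in secondary hypothesis 3 among the moderators, under "type of comorbidity (PTSD, time since injury, sleep, depression substance abuse, medication use", and again in secondary objective 3: "To evaluate other moderators of response to rTMS treatment such as age, time since injury and severity of PTSD".

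**Timing.** The primary hypothesis compares baseline with post-treatment. Sections 2a and 8m put the 20 sessions over 2 to 6 weeks, and section 2a allows compression to 1.5 weeks. Section 8d of the resources text (sufficient time) puts the late visit at 26 weeks after treatment.

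**The concern.** On the protocol's own account, how long ago a mild TBI occurred predicts how much a participant will improve without treatment. Someone enrolled soon after 2 months may improve between baseline and post-treatment, and may have recovered fully by the late visit, in either arm. Someone injured years earlier is expected to change little. Mixing the two groups widens the spread of change scores. If by chance one arm receives more recent injuries, the arm difference moves for a reason unrelated to stimulation.

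Adjusting for a strong prognostic variable removes both problems cheaply. The protocol does name covariates, in the passage that describes natural recovery, but leaves this one out. Naming it as a moderator is a different commitment: it asks whether the treatment effect varies with time since injury, and does not oblige the main comparisons to adjust for it.

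**Working it through.** The protocol gives no sample-size calculation, SD or effect size, so there is no figure of its own to reproduce. What follows is an illustration on a continuous change score.

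**1. Calendar, from the documents.** Entry just after 2 months, plus 2 to 6 weeks of treatment (0.46 to 1.38 months), puts the post-treatment test at 2.46 to 3.38 months after injury. Adding 26 weeks (6.0 months) puts the late visit at 8.5 to 9.4 months. The first test falls before or early in the 3-6 month period, and the late visit falls after it.

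**2. Assumptions, none from the documents.** Share of early mild entrants p = 0.3. Total spontaneous gain g = 0.5 to 1.0 SD. Test-retest correlation 0.7, so the variance of change without recovery is 2(1 − 0.7) = 0.6. Recovery is linear from month 2.

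**3. Added variance.** If early entrants gain d between the two tests and the others gain nothing, the added variance is p(1 − p)d² = 0.21d².

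| Comparison | d (SD) | 0.21d² | Rise over 0.6 |
|---|---|---|---|
| 2 weeks, recovery ends month 6 | 0.06–0.12 | 0.0007–0.0028 | 0.1–0.5% |
| 6 weeks, recovery ends month 6 | 0.17–0.35 | 0.006–0.025 | 1–4% |
| 2 weeks, recovery ends month 3 | 0.23–0.46 | 0.011–0.045 | 2–7% |
| 6 weeks, recovery ends month 3 | 0.5–1.0 | 0.0525–0.21 | 9–35% |
| 26-week visit, recovery complete | 0.5–1.0 | 0.0525–0.21 | 9–35% |

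For example, in the first row d = g × 0.46/4. A rise of 8.75% to 35% is equivalent to losing 1 − 1/1.0875 = 8% to 1 − 1/1.35 = 26% of the sample.

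**4. Chance imbalance.** The probability that the arms differ by 20 percentage points or more in the share of early entrants, at p = 0.3:

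- 20 per arm: 23% (two independent binomials) or 30% (hypergeometric, 12 early entrants among 40).
- 50 per arm: 4% or 5% by the same two methods.

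Both sizes are shown because the protocol gives 40 participants in sections 8g and 9d and 100 in sections 1a and 8a.

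**5. What an imbalance does.** A 20-point imbalance shifts the arm difference by 0.2d. At the late visit that is 0.10 to 0.20 SD, against a standard error of √(2 × 0.6/20) = 0.24 SD at 20 per arm. For the primary comparison with recovery to month 6, the shift is 0.01 SD (2 weeks, g = 0.5) to 0.07 SD (6 weeks, g = 1.0).

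**The case against.** **The covariate set belongs in a statistical analysis plan, which is not shown.** This is largely fair. Section 9a is a risk section, the comorbidities are introduced as examples, and the list does not claim to be complete. Its silence does not prove that the main analysis will ignore time since injury. What stands is narrower: the protocol chose to name covariates beside its recovery statement, and the variable that statement makes prognostic is not one of them.

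**Time since injury is already foreseen.** It is, as a moderator in two places. A moderator model would normally include its main effect, but it is a secondary analysis and does not define the main comparisons.

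**The effect may be trivial.** For the primary comparison this is right unless recovery is fast. The share of early entrants is unknown. The recovery statement covers mild TBI only, and recruitment also draws on patients from various conflict eras (resources section, access to target population) and on memory and other VA clinics.

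**Stronger readings a reader might infer.** One is that natural recovery biases the treatment comparison. It does not on average, because both arms are randomised and recover alike. Another is that covariate adjustment would rescue a durable benefit obscured by recovered sham participants. It would not: if the effect shrinks among people who recover anyway, a main-effect covariate or stratification leaves that dilution in place. Only the interaction or a subgroup estimate can show it, and the planned moderator analysis provides for that. Nor is 2 months inside the stated recovery period. It lies before it, which is why the point is worded as entry before recovery is expected to be complete.

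**Conclusion.** The point holds as a minor improvement to a stated list. Mild TBI participants may enter before the protocol expects recovery to be complete, and the named covariates omit the variable that tracks it.

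The cost is precision and chance imbalance, not average bias. For the primary comparison the added variance is about 0.1% to 4% if recovery runs to month 6, and reaches 9% to 35% only with recovery complete by month 3 and a 6-week course. At the 6-month visit the 9% to 35% range applies. Imbalance matters mainly with 40 participants; with 100 it is uncommon.

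All these sizes rest on the assumed 30% share, 0.5 to 1.0 SD gain, 0.7 correlation and linear recovery. If early entrants are few or gain little, the effect is negligible.

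**What to change.** Add time since injury to the covariates named in section 9a, for both the post-treatment and the 6-month comparisons, and say in what form it enters (for example, under versus at least 6 months). Leave the entry rule as it is, and keep the moderator analysis for the separate question of whether benefit differs between recent and older injuries. If a statistical analysis plan already adjusts for time since injury, a cross-reference is enough.

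The cost is one sentence. The variable is already needed for the exclusion criterion and the moderator analysis, so no new data, visits or participants are required.
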